8.7. Data analysis

8.7.1. Essential analysis

A stepwise approach will be used for the analysis: The initial analysis will be descriptive and unadjusted. Where numbers permit, multivariable analyses will be conducted for the primary and secondary analyses to adjust for possible confounders.

Statistical methods:

A detailed SAP will be prepared and finalized prior to the conduct of any study analysis. Patient characteristics will be summarized within each cohort for the interim and final reports.

Table 6 summarizes the exposure window for each outcome.

Table 6 Summary of Exposure Window for Each Outcome

Outcome	Exposure Window
Major Birth Defects	3 months prior to LMP to the end of the 1 st trimester
Minor Birth Defects	3 months prior to LMP to the end of the 1 st trimester
Spontaneous Abortion/Miscarriage	3 months prior to LMP to prior to 20.0 weeks' gestation
Preterm Delivery	3 months prior to LMP to prior to 37.0 weeks' gestation
Other Outcomes	3 months prior to LMP to the end of the pregnancy

For the primary endpoint, the exposure of interest is belimumab exposure in the pre-conception/first trimester period. For this study, this exposure is defined as any dose from 3 months prior to the 1st day of LMP and up to 13 weeks after the 1st day of the LMP. The primary comparison will be on the rate of major birth defects between Cohort 1 and Cohort 2 among pregnancies resulting in at least one live born infant. A point estimate of the crude (i.e. unadjusted) RR of Cohort 1 versus Cohort 2, as well as its 95% confidence intervals (CIs) will be computed.

The comparison will also be carried out within each of two strata, according to whether the woman had prenatal diagnostic testing, such as level II ultrasound, amniocentesis or chorionic villus sampling, prior to enrollment in the study or not.

The same analysis will be repeated using the second numerator and denominator encompassing pregnancies ending in at least one live births, stillbirth, spontaneous abortion or elective termination, but excluding those lost-to-follow-up.

Due to the observational nature of the study, the above crude estimate of RR will be further adjusted for potential confounders, provided that there are sufficient number of events. A complete list of potential confounders will be provided in a separate table for each outcome prior to the final analysis, based on scientific knowledge including literature review. In addition, all of the following three criteria will be applied in

accordance with the definition of confounders, and variables will be considered in a step-wise approach where any of these criteria are met: 1) by assessing each considered variable in a logistic regression model containing exposure and the outcome to determine if inclusion of that single covariate changes the estimate of the odds ratio for exposure by 10% or more; 2) standardized mean differences (SMD) greater than 0.1; 3) association with the outcome with p-value <0.2 in the unexposed group. Care will be taken not to include those variables that are strongly associated with the exposure but only weakly associated with the outcome.

The confounders identified above may be used to build the propensity score (PS) for exposure [Rosenbaum, 2002]. R package ‘twang’ or similar R package available at the time of analysis will be used for this purpose, following which SMD will be used to check the balance of the covariates between the cohorts.

The primary analysis will be performed with inverse probability weighting (IPW) using the propensity score. In the IPW approach, we will use stabilized weights that are further trimmed to be between 0.1 and 10 if necessary [Peter, 2015]. The robust sandwich variance estimator will be used following the IPW approach.

A secondary analysis will be conducted using outcome regression, i.e. a logistic regression model will be fitted with major structural defect (Y) as outcome, and exposure (A) and propensity score (L) as regressors. Standardization will be performed to obtain the estimated causal risk ratio [Hernán, 2019], which has the interpretation as the marginal or population averaged risk ratio. The CIs are obtained by 10,000 bootstraps.

For the secondary endpoints

The ideal pregnancy cohort would enroll women at conception, before any outcome, and then follow them for years after delivery. However, this is unrealistic for logistical reasons. Therefore, outcomes that must account for gestational age at enrollment (e.g. SAB) will have left truncation and right censoring. Left truncation occurs because participants enroll after conception and, therefore, after some outcomes may have already occurred. Right censoring occurs when there are enrolled pregnancies with unknown

outcomes due to lost to follow-up, pregnancy miscarriages, or terminations or stillbirths without fetal autopsy. Left truncation (late enrollment) may underestimate the risk of early pregnancy events (e.g., miscarriages, maternal death). Differences in gestational age at enrollment between exposed and reference groups could lead to biased relative risk estimates if the risk varies with gestational age. To prevent this bias, the most useful approach is to enroll subjects as early in their pregnancy as possible before outcomes can be expected and to begin follow-up of exposed and unexposed pregnancies at comparable gestational ages.

Specifically, the analysis of SAB and stillbirths is complicated by left truncation in the data, i.e., women enter the study at arbitrary times in gestation, and analyses of these outcomes must account for gestational age at enrollment. Only those women who are enrolled prior to 20.0 weeks of gestation are eligible for the analysis of SAB. Since they are not followed from gestational age zero, survival analysis methods will be used to handle left truncation, measuring time relative to enrollment, as well as right-censoring when a subject is lost-to-follow-up prior to 20.0 weeks' gestation. Left-truncated Kaplan-Meier estimate at 20.0 weeks' gestation will be used to estimate the spontaneous abortion rate in each of the cohorts with 95% CIs [Tsai, 1987]. The Cox proportional hazards regression models incorporating left truncation will be used to estimate the hazard ratio (HR) and 95% CIs of both cohorts. The individual group hazards and 95% CIs will also be presented. Stillbirth will be analyzed with a similar method.

To account for potential confounding, propensity score methods described above will be applied. In particular, regression adjustment will be used with the Cox model to obtain the adjusted HR.

The analysis of preterm delivery can also be complicated by left truncation in the data, i.e., women enter the study at arbitrary times in gestation. Only those women who are enrolled prior to 37.0 weeks of gestation are eligible for the analysis of preterm delivery. These data will be analyzed similarly to spontaneous abortion as described above using survival analysis methods, to handle possible left truncation and right-censoring.

Endpoints relevant to SGA at birth and postnatal growth deficiency at about 1 year of age in weight, height and head circumference (excluding multiple births) are all binary endpoints. The analysis of each of these outcomes will be similar to the analysis of the primary outcome.

Multiple births will be included in the analyses of minor structural defects, developmental concerns and serious infections. The outcome variables thus contain likely correlated data, and the generalized estimating equations (GEE) approach will be used to estimate the crude RR with 95% CI. The causal effect will be estimated similar to the primary outcome, but in place of logistic regression it will be GEE with the logistic link function. The CIs are obtained by 10,000 bootstraps, where the mothers (not infants) will be resampled with replacement.

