8.5. Study size

The proposed sample sizes in each of the study groups are as follows:

- 200 women exposed to belimumab at any time from 3 months prior to the first day of LMP through the end of pregnancy
- 200 women with SLE, unexposed to belimumab

An enrollment of 200 participants in each of the cohort groups is planned over 5 years. Based on previous experience with the MotherToBaby/OTIS Autoimmune Diseases in Pregnancy Project, the expected proportion of women to enroll in first trimester is approximately 70% [Chambers, 2019a]. It is estimated that participants will be an average of 7-10 weeks post-LMP at the time of enrollment. Given this mean gestational timing at enrollment, the anticipated live-birth rate is 85%, which includes a spontaneous abortion and elective abortion rate of 10% [Wilcox, 1988; Zinaman, 1996; Kanmaz, 2019; Chambers, 2019a] and an estimated lost to follow-up rate of 5% [Chambers, 2018], this will result in 170 pregnancies with at least one live born infant in each cohort at the end of recruitment. As a conservative estimate, the power calculations were also conducted assuming a live-birth rate of 80%, which includes a spontaneous abortion and elective abortion rate of 15% [Chambers, 2016], and an estimated lost to follow-up rate of 5%. This conservative estimate will result in 160 pregnancies with at least one live born infant in each cohort at the end of recruitment.

This study is designed to serve as an early warning system to identify a previously unrecognized major teratogen by identifying major birth defects in infants of exposed mothers. For less potent teratogens or for drugs and biological products that cause other adverse pregnancy outcomes, the study can function as a signal detection study and generate hypotheses that can be tested in other studies using other methods that may be better powered to assess these outcomes (FDA, 2019).

Table 4 gives the minimum detectable effect sizes with 80% power [two-sided significance level 0.05]) for the primary outcome of major birth defects. Table 4 includes

varying expected live births in each cohort, using varying rates of SAB/elective terminations and includes varying background rates of major birth defects, based on existing literature on pregnant women with SLE [Vinet, 2012; Gladman, 2010]. As a reference, the effect size has also been calculated based on the general population background rate of major birth defects of 2.8% in the Atlanta metropolitan area [CDC, 2017].

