to when women would typically enroll in the study. However, based on expected gestational timing of enrollment, spontaneous abortion rates in late first trimester and early second trimester will be analyzable. Further, measurement of a rare outcome may also limit the ability to adjust for potential confounders in multivariable analyses. Where possible due to sufficient events, a propensity score is planned to include relevant confounders.

A bias of this study might be associated with right truncation or censoring. This occurs when pregnancies end the follow-up before the outcome is known (censoring), or with unknown outcomes (truncation). Since pathology is rarely available for spontaneous abortions and terminations for social reasons, most cohorts consider the prevalence of malformations in livebirths rather than the cumulative incidence over gestation. Failure to include defects detected among terminations can underestimate the incidence of malformations and decrease power but, if the missingness is random with respect to exposure, the relative risk for malformations will be unbiased. Additionally, for other outcomes that are also dependent on timing of enrollment in relation to the outcome occurrence (e.g. elective termination and ectopic/molar pregnancy) there may be incomplete data. The dysmorphology exam for minor birth defects may not be performed consistently across all infants and thus there may be missing data for some infants. Medical records may also not be available for all women or infants and there could be missing data from these sources as well. Efforts will be made to enroll a disease comparison group that is of similar disease severity however, there could be differences between the cohorts that may not be able to be adjusted or accounted for due to the nature and collection of the data.

Strengths of the study design are the ability to build on the referral network of OTIS member services across the U.S. and Canada to identify belimumab-exposed pregnancies as well as appropriate comparison group pregnancies, the OTIS research groups' track record of excellent subject retention (<5% lost to follow-up) [[Chambers, 2010](#); [Chambers, 2016](#); [Chambers, 2019b](#)]. In addition, the study design allows for appropriate comparison to a treated disease group, and for appropriate attention to confounding or effect modification.

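### Each cohort's spontaneous-abortion rate is a left-truncated Kaplan-Meier estimate with no common starting week or minimum risk set, so one or two very early losses can dominate it

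*Protocol*

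**What the plan says.** Protocol 8.7.1 restricts the analysis set: "Only those women who are enrolled prior to 20.0 weeks of gestation are eligible for the analysis of SAB". It then fixes the reported rate: "Left-truncated Kaplan-Meier estimate at 20.0 weeks' gestation will be used to estimate the spontaneous abortion rate in each of the cohorts", with 95% CIs. The cohorts are compared by a hazard ratio: "The Cox proportional hazards regression models incorporating left truncation will be used to estimate the hazard ratio (HR) and 95% CIs of both cohorts".

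On the time axis the section says only that "survival analysis methods will be used to handle left truncation, measuring time relative to enrollment". That does not fit a curve read at 20.0 weeks' gestation, and the two statements need reconciling. No starting week, minimum risk set or conditioning statement is given for the rate.

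The section recognises the hazard of unequal entry: "Differences in gestational age at enrollment between exposed and reference groups could lead to biased relative risk estimates if the risk varies with gestational age". Its answer is to enrol early and to "begin follow-up of exposed and unexposed pregnancies at comparable gestational ages". That is an aim for enrolment, not a rule for the estimate.

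Section 8.5 expects that "participants will be an average of 7-10 weeks post-LMP at the time of enrollment". Section 8.9 says the highest spontaneous-abortion risk comes before women would typically enrol, and that "based on expected gestational timing of enrollment, spontaneous abortion rates in late first trimester and early second trimester will be analyzable".

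**The concern.** Under left truncation the Kaplan-Meier product begins at the first woman's entry. Few women will have enrolled by weeks 4-6, and by the protocol's own account loss risk is high then. A single loss in a risk set of three to five women moves the whole curve, and no later information can correct it. The cohort rate and its CI then largely reflect chance among a handful of very early enrollees.

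The rate also means risk to 20.0 weeks given a pregnancy still ongoing at that cohort's first entry. If the two cohorts' first entries differ, the two rates do not measure the same quantity, and nothing in the planned display would say so. Readers will set the two rates side by side even though the formal comparison is the hazard ratio.

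**Working it through.** **Inputs from the protocol.** Target enrolment is 200 per cohort. For spontaneous abortion, 5% elective abortion and 5% loss to follow-up are allowed, the background rate is 10%, and two-sided alpha 0.05 with 80% power gives a detectable ratio of 2.1 (8.5). Mean entry is 7-10 weeks, with about 70% enrolling in the first trimester (8.5).

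**The plan's own figure.** 200 x (1 - 0.05 - 0.05) = 180. With n = [1.96 x sqrt(2pq) + 0.842 x sqrt(p0q0 + p1q1)]^2 / (p1 - p0)^2, where p is the mean of p0 and p1 and q = 1 - p, taking p0 = 0.10 and p1 = 0.206 gives n of about 180. The detectable ratio is 2.06, which rounds to the stated 2.1. The sample-size figure is sound. The point concerns the estimator.

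**Leverage of one early loss.** The estimate is 1 - product of (1 - d/r) over loss times up to 20.0 weeks, where d is losses and r is women enrolled and still at risk. Take one early loss followed by a later risk of 10%. The last column is the early loss's Greenwood contribution to the SE, S x sqrt(d / (r(r - d))).

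| r at the early loss | Estimated rate | SE from that loss alone |
|---|---|---|
| 3 | 1 - (2/3)(0.90) = 40% | 0.60 x sqrt(1/6) = 24 points |
| 5 | 1 - (4/5)(0.90) = 28% | 0.72 x sqrt(1/20) = 16 points |
| 100 | 1 - (99/100)(0.90) = 10.9% | 0.891 x sqrt(1/9900) = 0.9 points |

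**Simulation.** The documents give neither the entry distribution nor the weekly hazard, so both are assumed:
- Entry is 4 weeks plus a gamma variable.
- Weekly hazard falls from 4% at week 4 to 0.2% at week 19.
- There is no other loss before week 20.
- Each setting has 2,000 cohorts.

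SDs and differences are in percentage points. The difference is the 95th percentile of the absolute gap between two cohorts with identical hazards and identical entry curves.

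| Mean (SD) entry, weeks; N | Median at risk, weeks 5 / 6 / 8 | SD from earliest entry / week 6 / week 8 | 95th percentile gap, same starts |
|---|---|---|---|
| 7.5 (2.5); 180 | 21 / 56 / 114 | 7.5 / 3.2 / 2.3 | 19.9 / 8.6 / 6.4 |
| 8.5 (3.0); 180 | 10 / 35 / 90 | 9.7 / 3.5 / 2.4 | 24.9 / 9.6 / 6.8 |
| 10 (3.5); 180 | 3 / 15 / 57 | 12.7 / 4.4 / 2.7 | 32.8 / 12.1 / 7.3 |
| 10 (3.5); 150 | 2 / 12 / 48 | 12.0 / 5.0 / 2.9 | 33.8 / 13.9 / 8.0 |

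Part of the fall in SD arises because a later start leaves a smaller risk to estimate. The relative SD still falls, from 39-71% (earliest entry) to 24-37% (week 6) or 27-35% (week 8). At the first loss the median risk set was 25-34 women, with a 2.5th percentile of 3-5.

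Further simulations used 180 per cohort, other assumed curves and a start at the first week with at least 20 at risk in both cohorts. There the SD was 2-4 points. Identical cohorts differed by more than 10 points in 1-8% of runs, against 13-42% from earliest entry.

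**Different risk periods.** Under the assumed hazards, true risk to week 20 is 19.6% from week 4, 16.2% from week 5, 13.2% from week 6 and 8.2% from week 8. With equal hazards, first entries at weeks 4 and 5 give a ratio of 19.6/16.2 = 1.21, and weeks 4 and 6 give 0.1956/0.1317 = 1.49. Simulated two-week gaps under other curves gave 1.5-1.7.

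**The planned comparison.** With first entries at weeks 4 and 6, median entries at weeks 8 and 10 and equal hazards, the median delayed-entry Cox hazard ratio was 1.00-1.02, and nominal 5% tests rejected in 3-5% of runs.

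**The case against.** The strongest reply is that the starting week is detail for the SAP, which is not shown and may set one. The protocol does not write that the curve starts at each cohort's earliest entry; that follows from the standard form of the named estimator. This stands as a limit on the claim. It does not remove it, because 8.7.1 fixes the estimator and its reading point, and following it as named gives a materially worse rate than a conditional one.

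Three stronger readings are tempting, and the documents do not support them.
- **That the planned comparison would show a false spontaneous-abortion signal.** The comparison is the left-truncated Cox hazard ratio, crude and propensity-adjusted. It compares women at the same gestational age and gives small early risk sets little weight. No ratio or test of the two Kaplan-Meier rates is planned.
- **That the two rates necessarily measure different periods.** This holds only if first entries differ. Both cohorts come through the same referral network, and 8.9 monitors comparability of enrolment timing (against recall bias). With similar enrolment, simulated first entries mostly lay within about a week. The label's request to register as soon as pregnancy is known (8.2.2) could bring exposed women in earlier, but the protocol gives no figure for a gap.
- **That 8.9 limits analysis to late first and early second trimester losses.** It says those rates can be analysed and that the study is limited for earlier losses. It does not say only.

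It is also fair that a first-loss risk set of two or fewer is a tail event, seen in 1-4% of simulated runs.

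**Conclusion.** The concern holds for the reported cohort rates and their CIs, and should be corrected. Run in standard form, the 8.7.1 estimator has an SD of about 8-13 points, against 2-4 points from a common start with at least 20 women at risk per cohort. This instability arises even when both cohorts enrol identically. A ratio of about 1.5-1.7 between the displayed rates, with no true difference, needs a two-week gap in first entry, which is an assumption and not a protocol figure. The left-truncated Cox hazard ratio is not materially affected.

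The sizes rest on assumed entry and hazard curves. The tabulated settings put 84-97% of women in the first trimester, against the roughly 70% in 8.5, so early risk sets could be larger or smaller than shown. The direction and order of size were the same under every set of curves tried.

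**What to change.** In 8.7.1, and carried into the SAP:
- State that the time scale for the spontaneous-abortion analysis is gestational age with delayed entry, and reconcile the wording about time relative to enrolment.
- Estimate risk from one common starting week w to 20.0 weeks in both cohorts. Fix w from enrolment data alone, before outcomes are tabulated: for example, the first completed week with at least 20 women at risk in each cohort, or a prespecified fixed week.
- Label the result as risk from w to 20.0 weeks given ongoing pregnancy at w, and show the number at risk at w.
- List losses before w separately by cohort.
- Keep the delayed-entry Cox model on all eligible women.

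The cost is a sentence or two of text, with no change to enrolment or data collection. The reported rate no longer covers the few weeks before w, where 8.9 already concedes limited ability, and the threshold for w is a convention.

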In addition to challenges to maternal health, patients with lupus have poor obstetric outcomes compared with women without SLE, including a greater likelihood of fetal loss (approximately 3-fold increase) and a greater incidence of preterm deliveries [~40% vs. 10% among healthy women] [Clark, 2003; Clowse, 2005]. Recently a meta-analysis addressing this subject was reported [Smyth, 2010]. The proportion of pregnancies in women with SLE resulting in fetal death has been reported to be 15%-20% in European studies [Cortes-Hernandez, 2002; Julkunen, 1993] and 15%-25% in North American

studies [Clowse, 2005; Andrade, 2008], with stillbirths accounting for 2%-4% of these outcomes.

The presence of anti-phospholipid antibodies has been reported in 30%-80% of patients with SLE [Mecacci, 2009], and is associated with an increased risk of spontaneous miscarriage and poor maternal and/or fetal outcome [Cortes-Hernandez, 2002; Clark, 2007]. In prospectively examined pregnancies, with anti-Ro and anti-La antibodies in the mother, the prevalence of congenital heart block (with mortality of approximately 20%-30%) is between 1% and 5%, and rises to between 6% and 25% when another pregnancy was affected in the same mother [Jaeggi, 2010; Friedman, 2010]. Active SLE and associated comorbidities (proteinuria, anti-phospholipid syndrome, thrombocytopenia, and hypertension) have also been noted to be important predictors of fetal loss [Clowse, 2006; Cortes-Hernandez, 2002; Julkunen, 1993].

A cohort of SLE pregnancies from a single academic medical center in the US identified risk factors for fetal loss and pre-term delivery. Among pregnant patients with high SLE disease activity (Physician Global Assessment [PGA] score ≥ 2), 42% had fetal loss during the first trimester compared to 14% among women with low activity (PGA < 2). Same pattern was observed during the second (32% vs. 7%, respectively) and third trimesters (10% vs. <1%, respectively) among pregnant patients with high SLE disease activity vs. women with low activity. The combination of high disease activity, with low complement and/or anti-ds DNA auto antibodies, during the second trimester increased the risk of fetal loss and preterm delivery pregnancy outcomes [Clowse, 2011].

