
Spontaneous abortion (SAB)
	
Defined as spontaneous pregnancy loss prior to 20 weeks' gestation (including ectopic/molar pregnancy). In this study, since women enroll after recognition of pregnancy, SABs are only identified after enrollment in clinically recognized pregnancies. This outcome is reported by the mother and validated through the medical record, where available.
	
Pregnancies
	
Included counted as one case if all multiple pregnancies ended in SAB. Pregnancy is counted as a live birth outcome if at least one pregnancy resulted in a live-born infant
	
Up to 20 weeks gestation
	
Prior to 20 weeks gestation
	
Cohort 1: SAB among all pregnancies enrolled in the study prior to 20 weeks' gestation with exposure at any time in pregnancy³ prior to 20 weeks and with at least 1 follow-up data collection point after enrollment date
 
Cohort 2: SAB among all pregnancies enrolled in the study prior to 20 weeks' gestation with no exposure at any time in pregnancy³, with at least 1 follow-up data collection point after enrollment date

Stillbirth
	
Defined as a fetal death that occurs ≥ 20 weeks' gestation.
	
Pregnancies
	
Included counted as one case if all multiple pregnancies ended in stillbirth. Pregnancy is counted as a live birth outcome if at least one pregnancy resulted in a live-born infant
	
At birth
	
3 months prior to LMP and/or any time in pregnancy³ prior to outcome
	
Cohort 1: Stillbirths among all pregnancies¹ with exposure at any time in pregnancy³;
 
Cohort 2: Stillbirths among all pregnancies¹ with no exposure at any time in pregnancy³;

Outcome	General definition	Denominator	Pregnancy involving multiples	Outcome assessment	Exposure time	Endpoints

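### The Kaplan-Meier method for spontaneous abortion is carried over to stillbirth with no reading point and no handling of live birth as a competing event

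*Protocol*

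**What the plan says.** For spontaneous abortion, section 8.7.1 of the protocol is specific: "Left-truncated Kaplan-Meier estimate at 20.0 weeks' gestation will be used to estimate the spontaneous abortion rate in each of the cohorts", with 95% CIs. The text names "right-censoring when a subject is lost-to-follow-up prior to 20.0 weeks' gestation" as the censoring event and adds a left-truncated Cox model for the hazard ratio. For stillbirth the whole instruction is "Stillbirth will be analyzed with a similar method".

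The general description of censoring earlier in 8.7.1 reads "Right censoring occurs when there are enrolled pregnancies with unknown" outcomes. It goes on to list loss to follow-up and pregnancy losses or terminations without autopsy. Live birth is not in the list.

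Table 2 in section 8.3.2 gives the stillbirth definition as "Defined as a fetal death that occurs ≥ 20 weeks' gestation". The endpoint there is "Stillbirths among all pregnancies", and footnote 1 makes that denominator include live births, spontaneous abortions, elective terminations and stillbirths. Section 8.7.3 ties the final analysis to the methods of 8.7.1 and 8.7.2.

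**The concern.** Kaplan-Meier treats a censored subject as someone who could still have the event later. A pregnancy that has ended in live birth can no longer end in stillbirth, so live birth is a competing event. Before 20 weeks this hardly matters. From 20 weeks it decides what the curve means: with deliveries censored, 1 minus KM describes the stillbirth risk that would apply if nobody delivered.

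The absolute rate and CI in each cohort are at stake. They could come out too high and rest on the few women still undelivered at the end of gestation. They would also answer a different question from the Table 2 proportion, whose denominator includes pregnancies that ended before 20 weeks and were never at risk of stillbirth. Stillbirth is a named secondary outcome and, in section 11, one of the selected serious adverse events. With few events expected, one late case could move the reported rate a good deal.

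**Working it through.** The protocol states no stillbirth rate, power or expected event count for its own cohorts, so there is no figure to reproduce.

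**1. Does the template work for spontaneous abortion?** Section 8.5 gives 10% spontaneous abortion and 5% elective abortion. With constant hazards, the event-free share is 1 - 0.10 - 0.05 = 0.85, and 10/15 of the total hazard belongs to spontaneous abortion. Censoring terminations gives

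1 - KM = 1 - 0.85^(10/15) = 10.27%, against a true 10.0%.

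The shift is 0.27 points. With 180 pregnancies per cohort (section 8.5) the SE is √(0.10 × 0.90 / 180) = 2.2 points. The template is adequate there.

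**2. Inputs for stillbirth (assumptions).**
- Cumulative stillbirth risk of 3% from 20 weeks. This is the midpoint of the 2%-4% in section 6.1, read as a share of pregnancies.
- 165 pregnancies per cohort, midway between the 160 and 170 in section 8.5.
- Preterm share of 10% to 40%, from "a greater incidence of preterm deliveries [~40% vs. 10% among healthy women" in section 6.1.
- Weekly steps from week 20 to week 42 (23 steps), a constant weekly stillbirth hazard h, an assumed spread of delivery weeks, and live births censored at delivery.

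**3. Formulas.**
- Cumulative incidence by 42 weeks = h × (mean number of weekly steps at risk).
- 1 - KM at week w = 1 - (1 - h)^(w - 19).

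The cumulative incidence is fixed at 3%. A mean of about 19.4 steps at risk (10% preterm) gives h = 0.03 / 19.4 = 0.00155. A mean of about 17.4 (40% preterm) gives h = 0.03 / 17.4 = 0.00172.

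| Week | Steps | 1 - KM, 10% preterm | 1 - KM, 40% preterm | Cumulative incidence |
|---|---|---|---|---|
| 38 | 19 | 2.9% | 3.2% | 2.8-2.9% |
| 40 | 21 | 3.2% | 3.6% | about 3.0% |
| 42 | 23 | 3.5% | 3.9% | 3.0% |

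The excess at 40 weeks is therefore 0.2-0.6 points, and at 42 weeks 0.5-0.9 points. The SE of a plain proportion is √(0.03 × 0.97 / 165) = 1.33 points. At 40 weeks the excess is at most 0.6 / 1.33 = 0.45 SE. At 42 weeks it reaches 0.9 / 1.33 = 0.68 SE.

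**4. Sensitivity to the hazard.** If the hazard triples after 37 weeks (assumed), 1 - KM at 42 weeks is 4.2-4.9% for the same true 3%.

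**5. Stability.** About 11-17 of 165 pregnancies are still at risk in week 41, and 2-3 in week 42. One stillbirth in week 41 moves KM by roughly 1/17 to 1/11, or 6 to 9 points. The same event moves the cumulative incidence by 1/165 = 0.6 points. Another assumed delivery pattern with 180 pregnancies leaves 8-13 in week 41 and 1-2 in week 42, so the picture does not rest on one choice.

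**6. Denominator.** Suppose 10-15% of pregnancies end in spontaneous or elective abortion (section 8.5), all before 20 weeks. A 3% risk among those who reach 20 weeks then becomes 3% × 0.90 = 2.7% or 3% × 0.85 = 2.6% of all pregnancies.

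**The case against.** The strongest reply is that no passage says live births are censored. Section 8.7.1 lists unknown outcomes and loss to follow-up, and a live birth is a known outcome. If live-born pregnancies were carried forward event-free to a fixed week, the result would be a cumulative-incidence-type proportion without this bias. That stands: a reader might infer that the plan censors live births, but the text leaves this open.

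Second, a reading week and a competing-event rule are details that a statistical analysis plan can supply. That stands as far as missing detail goes. But the protocol does more than leave a blank. It names the estimator by reference to spontaneous abortion, and 8.7.3 commits the final analysis to it. The carry-over is unsuitable without a further rule.

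Third, the size depends on the reading week, and before 39 weeks it is slight. The 2%-4% is also ambiguous: it may mean a share of fetal deaths. With fetal death at 15%-25% (section 6.1), stillbirth would then be 0.15 × 0.02 = 0.3% to 0.25 × 0.04 = 1.0% of pregnancies. At 0.5% the excess at 42 weeks is about 0.1 points. Both stand.

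Fourth, the comparison between cohorts is a Cox hazard ratio. With live births censored it is a valid cause-specific hazard ratio. That stands in full.

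A reader might also infer that the two cohorts' rates could not be compared because of different preterm rates. The documents do not support this: the 40% against 10% contrasts women with SLE with healthy women, and both cohorts here have SLE. Even that full contrast moves the 42-week excess by only 0.9 - 0.5 = 0.4 points.

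**Conclusion.** The point holds in conditional form. The protocol extends a method suited to events before 20 weeks to an outcome whose risk period is when live birth removes almost every pregnancy. It sets no reading point and no competing-event rule. If live births are censored, 1 minus KM is biased upwards: under half an SE through 40 weeks with a constant hazard, more at 42 weeks or if the hazard rises near term. The main harm is instability from week 41.

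All sizes rest on an assumed 3% risk, on reading 2%-4% as a share of pregnancies, and on assumed delivery and hazard patterns. The documents do not establish that the reported rates will be wrong by a given amount, nor that the hazard ratio is invalid. This is a secondary outcome, so the matter is worth correcting but does not touch the primary analysis.

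**What to change.** In section 8.7.1, replace the single sentence on stillbirth. Estimate each cohort's rate by a left-truncated cumulative incidence (Aalen-Johansen) on gestational age from 20.0 weeks, with live birth and termination at 20 weeks or later as competing events and only loss to follow-up censored. Keep the Cox hazard ratio and label it cause-specific. In Table 2, change the stillbirth denominator to pregnancies ongoing and under observation at or after 20.0 weeks, so that the definition and the estimator describe the same quantity.

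The cost is a small amount of extra analysis wording. Standard software covers the method and no new data are needed.
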